11.3.4 Analysis of Safety Data

The summary of safety results will be presented by treatment group. All safety analyses will be performed on the safety population using the following common rules:

- The baseline value is defined generally as the last available value before randomization.
- Adverse event observation periods are defined as follows:
 - Pretreatment AEs are AEs that developed or worsened prior to the first dose of study drug

- On-treatment AEs are AEs that developed or worsened from the first dose of study drug to study completion/discontinuation. Summaries of TEAEs will include all on-treatment AEs.
- For quantitative safety parameters based on central laboratory/reading measurements descriptive statistics will be used to summarize results and change from baseline values by visit and treatment group.

11.3.4.1 *Adverse Events*

Treatment-emergent AEs, TEAEs assessed as related to study drug or to study procedures, and treatment-emergent SAEs will be summarized for each treatment group based on MedDRA coding of verbatim terms reported by Investigators.

Adverse event incidence tables will present, by system organ class (SOC) and preferred term, the number and percentage of patients experiencing an AE. Multiple occurrences of the same event will be counted once in the tables. The denominator for computation of percentages is the safety population within each treatment group.

Adverse event incidence tables will present, by SOC and preferred term, the number and percentage of patients experiencing an AE by severity and by relationship to treatment. In tabulating the severity of AEs, the highest severity will be assigned to a subject with more than one occurrence of the same AE. The highest level of association will be reported in subjects with differing relationships for the same AE.

Listings of all AEs, SAEs, deaths, and AEs leading to study discontinuation will be provided.

11.3.4.2 *Clinical Laboratory Evaluations*

Summary statistics of laboratory variables will be calculated for each visit or study assessment by treatment group. Shift tables showing the pattern of change from baseline to postbaseline visit(s) will be provided. Listings of laboratory data will be provided. For hematology and chemistry variables, the normal ranges will be provided, and abnormal laboratory values flagged and clinical significance indicated. A listing of clinically significant hematology and chemistry findings will be provided.

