Screening evaluations must be completed within 6 weeks of signing the informed consent form (ICF) and these assessments can occur on multiple days, provided they are within the Screening Period. The Investigator will determine whether patients meet eligibility criteria and will collect the demographic and medical data permitting full characterization of the patient. A baseline open muscle biopsy (from deltoid) will be collected at least 2 weeks prior to the Day 1 visit. This will allow full recovery from the surgery prior to obtaining baseline functional assessments (e.g. NSAA). All attempts should be made to complete all screening assessments and confirm patient eligibility for the study prior to muscle biopsy collection to prevent biopsies from being performed on patients not eligible for the study. The time from signing the ICF to Day 1, including screening and open muscle biopsy collection cannot exceed 6 weeks. Patients who screen fail for the first time may be rescreened once.

Double-blind Treatment Period

In the Double-blind Treatment Period, patients will receive weekly intravenous (IV) doses of either placebo or WVE-210201. Patients will be randomized in a 1:1:2:2 ratio to placebo 3 mg/kg, placebo 4.5 mg/kg, WVE-210201 3 mg/kg, and WVE-210201 4.5 mg/kg. Patients must be randomized within 1 day prior to their first dose.

Assessments of safety, efficacy, pharmacokinetics, and immunogenicity will be performed throughout the study.

A second open muscle biopsy (from deltoid) will be collected at 1 of the 3 time points below:

- First 30 patients: Week 12
- Next 40 patients: Week 22
- Remaining patients: Week 46, 2 weeks prior to Week 48 visit.

The biopsy timing facilitates interim analyses of dystrophin; all biopsies will be used in the primary efficacy analysis. The open muscle biopsies will be collected to allow for adequate tissue quantity and quality for analysis of dystrophin related study endpoints via Western blot and other pharmacodynamic assessment methods (e.g. immunohistochemistry, exon skipping via reverse transcription polymerase chain reaction [RT-PCR]).

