4.1.1 Screening

Screening evaluations must be completed within 6 weeks of signing the informed consent form (ICF) and these assessments can occur on multiple days, provided they are within the Screening Period. The Investigator will determine whether patients meet eligibility criteria and will collect the demographic and medical data permitting full characterization of the patient. Patients who screen fail may be rescreened once.

A record of patient screen failures will be maintained for patients who do not qualify for enrollment, including the reason for the failure. A baseline open muscle biopsy (from deltoid) will be performed at least 2 weeks prior to the Day 1 visit. This will allow full recovery from the surgery prior to obtaining baseline functional assessments. All attempts should be made to complete all screening assessments and confirm patient eligibility for the study prior to muscle biopsy collection to prevent biopsies from being performed on patients not eligible for the study. The time from signing the ICF to Day 1, including screening and open muscle biopsy collection cannot exceed 6 weeks.

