4.1.2 Double-blind Treatment Period

In the Double-blind Treatment Period, patients will receive weekly intravenous (IV) doses of either placebo or WVE-210201. Patients will be randomized in a 1:1:2:2 ratio to placebo 3 mg/kg, placebo 4.5 mg/kg, WVE-210201 3 mg/kg, and WVE-210201 4.5 mg/kg. Patients must be randomized within one day prior to their first dose. Safety and efficacy assessments will be performed over the course of study. All functional assessments, performance of upper limb (PUL), NSAA, myometry, timed function tests, and pulmonary function tests (peak flow rate [PFR], cough peak flow [CPF], and forced vital capacity [FVC]) and completion of the Pediatric Quality of Life questionnaires must be done pre-dose (on the dosing day or up to 24 hours prior to respective dosing day). The ActiMyo wearable device will also be given to patients, and activity data will be collected throughout the study at specified timepoints. To minimize the potential unblinding, functional assessments must be completed by an assessor not involved in administration of study drug or assessment and recording of AEs during the study. The same assessor should perform the functional assessments throughout the study for a given patient to minimize variability of assessments.

A second open muscle biopsy (deltoid) will be collected at 1 of 3 timepoints mentioned below:

- First 30 patients: Week 12
- Next 40 patients: Week 22
- Remaining patients: Week 46, 2 weeks prior to Week 48 visit.

The biopsy timing facilitates interim analyses of dystrophin; all biopsies will be used in the primary efficacy analysis. The open muscle biopsies will be collected to allow for adequate tissue quantity and quality for analysis of dystrophin-related study endpoints via Western blot analysis (dystrophin protein level), and other pharmacodynamic assessment methods (e.g., dystrophin localization by immunohistochemistry, exon skipping via RT-PCR).

In addition, pharmacokinetics of WVE-210201 will be determined. Immunogenicity analysis will also be performed.

Patients and parents will be asked to complete the quality of life questionnaires as applicable.

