^d **Weight will be collected pre-dose at screening, Day 1, Week 4 and every 4 weeks afterwards; the most recent weight collected is to be used to determine the infusion volume. Height will also be collected on those timepoints.**

^e Patient must rest quietly ≥ 5 minutes prior to collection of blood pressure (systolic and diastolic), pulse, or ECG. On Day 1 and Week 48 (D330), 12 lead (triplicate) ECG will be done pre-dose (within 24 hours), and 15 minutes (± 5 mins) after EOI.

^f Full panel (Table 9) collected at these time points. Platelets (footnote h), cardiac troponin I (footnote i), serum cystatin c (footnote k), complement, and coagulation parameters to be collected at additional time points as listed in the Schedule of Assessments.

^g Pre-dose platelet samples collected and analyzed locally. Abnormal results repeated locally for confirmation. Concurrent samples collected and sent centrally for analysis (Section 6.2.4.2)

^h Blood samples will be collected at screening and will be repeated if a patient's platelet count falls to $< 75,000$ platelets/ μ L (See Section 6.2.4.2 for details)

ⁱ Cardiac troponin I assessed at screening, baseline (Day 1 pre-dose), Weeks 6, 12 and 48.

^j Twenty-four-hour urine collection performed for all patients during Screening. Urinalysis (local urine dipstick and central quantitative urine) done pre-dose every dosing day. If urine protein on pre-dose quantitative testing is elevated > 0.2 mg/mOsm, dose should be held and a 24-hour urine collection and assessment be done. See Section 6.2.4.1 for all pre-dose parameters to be evaluated, including serum cystatin C.

Table 10

^k See protocol [Section 6.2.4.1](#) for all pre-dose parameters to be evaluated, including serum cystatin c.

^l Functional assessments will be done pre-dose on Weeks 1, 12, 24, 36, and 48 (on the dosing day or up to 24 hours prior to the indicated dosing day) These will not be assessed on Week 4. PedsQL will be collected pre-dose on Week 1 and Week 48 (on the dosing day or up to 24 hours prior to the indicated dosing day). See [Section 8.7.2](#) for sequence and timing of these assessments.

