8.1.8 Clinical Laboratory Evaluations

Clinical laboratory safety testing will be collected at the time points described in the Schedule of Assessments ([Table 1](#) and [Table 2](#)) and recorded in the eCRF and source documents. Safety laboratory samples will be analyzed at a central laboratory. Local testing on these samples may be conducted, as clinically indicated.

The parameters to be assessed are presented in [Table 9](#).

Table 9 Clinical Laboratory Parameters

| Hematology | Coagulation | Clinical chemistry | Urinalysis |
|--|--|--|--|
| 
Complete blood count, including:
 
 White blood cell count (with differential) Red blood cell count Hemoglobin Hematocrit Platelet count Reticulocyte count Mean corpuscular volume Mean corpuscular hemoglobin Mean corpuscular hemoglobin concentration High sensitivity C-reactive protein (hsCRP) Fibrinogen Complement (C3 and Bb)^a | 
Activated partial thromboplastin time
 
Prothrombin time
 
International Normalized Ratio
 | 
Sodium
 
Potassium
 
Chloride
 
Bicarbonate
 
Blood urea nitrogen
 
Creatinine
 
Creatine phosphokinase
 
Alanine aminotransferase
 
Aspartate aminotransferase
 
Alkaline phosphatase
 
Bilirubin
 
Gamma glutamyl transferase
 
GLDH
 
Serum Cystatin C
 
Hepatitis B surface antigen test^b
 
Hepatitis C antibody test^b
 
Cardiac Troponin 1
 | 
pH
 
Specific gravity
 
Urine osmolality
 
Glucose
 
Ketones
 
Blood
 
Urobilinogen
 
Bilirubin
 
Microscopic examination for RBCs and WBCs
 
Quantitative analysis of protein
 |

^a Complement will not be tested at Screening.

^b Tested only at Screening

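### The safety baseline is tied to randomization, which may come before the Day 1 pre-dose tests; complement and possibly ECG can then lack a baseline, and other laboratory tests fall back to Screening

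*Combined protocol and SAP*

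**What the plan says.** The common rules for safety analyses in Section 11.3.4 include this definition: "The baseline value is defined generally as the last available value before randomization". The same section plans change-from-baseline summaries by visit and treatment group for centrally measured or centrally read quantitative safety parameters. Section 11.3.4.2 adds shift tables for laboratory variables. Safety laboratory samples are analyzed centrally (Section 8.1.8) and ECGs are read centrally (Section 8.1.6), so both come under the rule.

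On the timing of randomization, Section 4.1.2 says: "Patients must be randomized within one day prior to their first dose". The synopsis has the same rule.

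The Day 1 tests are tied to dosing, not to randomization:

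- Urine, Table 1 footnote j: "Urinalysis (local urine dipstick and central quantitative urine) done pre-dose every dosing day".
- ECG, Table 1 footnote e: "On Day 1 and Week 48 (D330), 12 lead (triplicate) ECG will be done pre-dose (within 24 hours".
- Troponin, Table 1 footnote i: "Cardiac troponin I assessed at screening, baseline (Day 1 pre-dose), Weeks 6, 12 and 48".
- Complement, Table 9 footnote a: "Complement will not be tested at Screening".

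The ECG row of Table 1 has no Screening entry.

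**The concern.** The definition uses one time anchor and the schedule uses another. If a boy is randomized the day before dosing, or on Day 1 before his samples are drawn, his Day 1 pre-dose values come after randomization and the rule does not count them as baseline. The cost is more than the day or less between randomization and dosing, because the preceding value is the Screening value or, for some tests, no value at all.

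Complement is where this matters most. Section 1.3 reports complement rises in monkeys and one high-dose animal whose euthanasia was attributed to probable complement-mediated toxicity. The trial samples complement on Day 1, Day 2 and Day 8, and a change over those days cannot be tabulated without a baseline. Kidney and liver are the other main nonclinical findings. Their changes would be measured from a value taken before an open muscle biopsy, and the age of that value would differ from boy to boy according to when sites randomize.

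**Working it through.** The plan states no figure for this point, so there is none to reproduce. The check compares the timeline with the schedule.

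**Step 1. Randomization window.** Randomization falls 0 to 1 day before first dose (synopsis; Section 4.1.2). No section requires the Day 1 tests to precede it, and none gives a substitute baseline. Urinalysis is done on the dosing day, so for a boy randomized the day before, it necessarily follows randomization.

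**Step 2. What remains if the Day 1 values are excluded** (Table 1 with footnotes, Table 9, Section 6.2.4).

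| Test | Screening value | Day 1 stated as pre-dose | Baseline under the rule |
|---|---|---|---|
| Complement | No | Not stated | None |
| ECG | No | Yes, within 24 hours | None, unless recorded before randomization |
| Troponin, platelets, urinalysis, cystatin C | Yes | Yes | Screening |
| Hematology, chemistry, coagulation | Yes | Not stated | Screening |

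**Step 3. Age of the Screening value.**

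- Upper limit, Section 4.1.1: "The time from signing the ICF to Day 1, including screening and open muscle biopsy collection cannot exceed 6 weeks". That is 6 × 7 = 42 days before Day 1.
- Lower limit: Table 1 footnote a puts Screening before the biopsy, and footnote b puts the biopsy at least 2 weeks before Day 1. That is 2 × 7 = 14 days.
- Age at first dose is therefore about 14 to 42 days. At a randomization one day earlier it is 14 − 1 = 13 to 42 − 1 = 41 days.

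The lower limit is approximate, because Section 4.1.1 words completion of screening before biopsy as something to be attempted. An unscheduled sample between Screening and randomization would also shorten the gap.

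**Step 4. Consistency with the rest of the plan.** Footnote i calls the Day 1 pre-dose troponin value the baseline. Section 11.3.4 itself divides pretreatment from on-treatment adverse events at the first dose. Section 9 defines treatment-emergent events by exposure, and the safety population in Section 11.2.1 requires a dose. The baseline rule is the only one of these anchored on randomization.

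**Step 5. Result with a first-dose anchor.** Every Day 1 pre-dose value counts, whenever randomization occurred. ECG has a baseline, and so does complement if its Day 1 sample is drawn pre-dose. The other tests use a value 0 to 1 day old instead of about 14 to 42 days old.

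**The case against.** The strongest reply is that the rule is hedged. It says *generally*, and the troponin footnote could be read as one of the exceptions that word allows, in which case Day 1 pre-dose may already be the working baseline. The protocol also sends statistical detail to a SAP (Sections 11.5.1 and 11.5.2), and a refinement there could not be checked because no separate SAP text is reproduced in the public document. This softens the point but does not remove it: the text gives no exception for complement, ECG or the other laboratory tests.

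A reader might also infer more than the documents support:

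- **That every ECG baseline is lost for the boys affected.** The 24-hour pre-dose window allows an ECG before randomization even when randomization is on the day before dosing.
- **That safety data are lost or tables become impossible.** Day 1 values are collected whatever they are called, and Section 11.3.4.2 already summarizes laboratory variables by visit and lists them. The label can be corrected before database lock.
- **That most boys are affected.** If randomization follows Day 1 sampling, which is permitted, the problem does not arise. No section says which order sites will use.
- **That re-anchoring alone secures a complement baseline.** Table 1 does not say that the Day 1 complement sample is pre-dose.
- **That the arms are compared unfairly.** Treatment is randomized and blinded, so older baselines should fall similarly on all arms. They add noise and missing values, not an evident bias.

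The monkey finding should also be kept in proportion. The animal received 75 mg/kg over 30 minutes, and Section 1.3 describes monkeys as more sensitive to complement activation than humans.

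**Conclusion.** The point holds as a mismatch between the baseline definition and the schedule. For any boy randomized before his Day 1 samples, complement has no baseline under the rule, ECG may have none, and the other laboratory tests use Screening values about 14 to 42 days old that predate the biopsy. This assumes the rule is applied as written, Screening is completed before the biopsy, and no unscheduled samples intervene.

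The proportion of the roughly 150 boys affected could be anything from none to all, and the documents do not narrow that range. The consequence is limited to descriptive change-from-baseline summaries and, for laboratory variables, shift tables. It is a free improvement, worth making because complement, renal and hepatic changes are among the safety results the trial most needs to show clearly.

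**What to change.** 1. In Section 11.3.4, and in the SAP, define the safety-analysis baseline as the last non-missing value before the first dose of study drug.
2. In the Table 1 footnotes, state whether the Day 1 complement, hematology, chemistry and coagulation samples are pre-dose. Without this, the new definition does not by itself settle the complement baseline.
3. Section 6.2.4.1 uses cystatin C elevation from baseline in its dose-withholding criteria without defining that baseline. Those passages must be reconciled with whatever definition the protocol adopts. How they should read is a clinical matter and is left open here.

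The cost of the first two items is a line of wording and a footnote. No visit, sample, procedure or sample-size change is needed, and no efficacy analysis is altered.

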3 STUDY OBJECTIVES

3.1 Study Objectives-Double-blind Treatment Period

Primary Objectives

- To evaluate the efficacy of WVE-210201 by assessing changes in dystrophin levels (United States/Other regions as applicable)
- To evaluate the efficacy of WVE-210201 by assessing changes in motor function by North Star Ambulatory Assessment (NSAA) (EU/Japan)

Secondary Objectives

- To evaluate the efficacy of WVE-210201 by assessing changes in upper limb proximal strength
- To evaluate the efficacy of WVE-210201 by assessing changes in lower limb motor function
- To evaluate the efficacy of WVE-210201 by assessing changes in respiratory function
- To evaluate the efficacy of WVE-210201 by assessing changes in stride velocity
- To evaluate the safety of WVE-210201

Exploratory Objectives:

- To evaluate the efficacy of WVE-210201 by assessing changes in quality of life
- To assess the PK of WVE-210201 in plasma
- To evaluate the efficacy of WVE-210201 by assessing changes in upper limb function

- To evaluate the effect of WVE-210201 on dystrophin protein localization
- To evaluate the effect of WVE-210201 on exon-skipping
- To evaluate the efficacy of WVE-210201 by assessing changes in cardiac function (by echocardiogram [ECHO])
- To evaluate the efficacy of WVE-210201 by assessing changes in daily activity as measured by a wearable device
- To evaluate the efficacy of WVE-210201 by time to milestone events

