4.1.3 Open-label Treatment Period

After the Double-blind Treatment Period efficacy assessments are completed pre-dose at Week 48, all patients will transition to the OL Treatment Period and receive WVE-210201. Patients randomized to WVE-210201 will continue with the dose administered at the end of the Double-blind Treatment Period. Patients randomized to placebo in the Double-blind period will be treated at the matching WVE-210201 dose level. During the OL Treatment Period, patients will remain blinded to the treatment they received in the Double-blind Treatment Period.

Assessments of safety, efficacy, pharmacokinetics, and immunogenicity will be performed during the OL Treatment Period.

At subsequent visits, all functional assessments, PUL, NSAA, myometry, timed function tests, and pulmonary function tests (PFR, CPF, FVC), must be performed pre-dose (on the dosing day or up to 24 hours prior to the respective dosing day). The pediatric quality of life questionnaires will also be completed.

Assessments of safety, pharmacokinetics, and immunogenicity will also be performed during the OL Period.

To minimize the potential unblinding, functional assessments must be completed by an assessor not involved in administration of study drug or assessment and recording of AEs during the study. The same assessor should perform the functional assessments throughout the study for a given patient to minimize variability of assessments.

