^m Refer to [Section 6.2.2](#)for details regarding study drug administration. Prior to dosing, review of drug withholding criteria should be performed (See [Section 6.2.4](#)). For each dosing day, ± 2 days of window may be allowed. However, administration of Study Drug needs to be separated by a minimum of 5 days between infusions. Starting from Week 48, all patients will receive WVE-210201.

Table 2 Schedule of Assessment-Open-label Treatment Period

| Assessments | Weekly Treatment Visit | | | | | | | | Follow-up ^a |
|--|------------------------|------|------|------|---------------------|----|-------|----|------------------------|
| | | | | | 50-51 | 52 | 53-59 | | |
| | | | | | | 60 | 61-71 | | |
| | | | | | | 72 | 73-83 | | |
| | | | | | | 84 | 85-95 | | |
| | | | | | | | | 96 | ET |
| Prior or concomitant medications | Refer to Table 1 | D330 | D331 | D337 | D338 (TC) | | | | |
| Physical examination ^b | | | X | X | X | X | X | X | X |
| Height ^c | | | | | Every 4 weeks | | | X | X |
| Weight ^c | | | | | Every 4 weeks | | | X | X |
| Vital signs ^d | | | X | X | X | X | X | X | X |
| ECG ^d | | | | | | | | X | X |
| Echocardiogram | | | | | | | | X | X |
| Hematology ^e | | | X | X | X | X | | X | X |
| Platelets ^f | | | | X | X | X | X | X | X |
| Anti-platelet antibody ^g | | | | | See Section 6.2.4.2 | | | | |
| Clinical Chemistry ^e | | | X | | | X | | X | X |
| Cardiac troponin I ^h | | | | | | X | X | X | X |
| Coagulation parameters | | | X | | | X | | X | X |
| Urinalysis ⁱ | | | | X | X | X | X | X | X |
| Serum cystatin C ^j | | | | X | X | X | X | X | X |
| Complement | | | X | X | X | X | | X | X |
| AE monitoring | | | X | X | X | X | | X | X |
| Pharmacokinetics | | | | | Table 5 | | | | |
| Immunogenicity sample | | | | | Table 7 | | | | |
| NSAA ^k | | | | | | X | | X | X |
| Pulmonary function testing ^k | | | | | | X | | X | X |
| PUL 2.0 ^k | | | | | | X | | X | X |
| Timed function test-4 stair climb ^k | | | | | | X | | X | X |
| Myometry ^k | | | | | | X | | X | X |
| PedsQL-Generic core scale a-child self-report and parent proxy report ^k | | | | | | | | X | X |
| PedsQL-Neuromuscular Module ^k | | | | | | | | X | X |
| Treatment (WVE-210201) ^l | | | | X | X | X | X | X | X |

Abbreviations: ECG=electrocardiogram, EOI=end of infusion, ICF=informed consent form, NSAA=North Star Ambulatory Assessments.

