9 ADVERSE EVENTS

The Investigator is responsible for reporting all AEs that are observed or reported during the study, regardless of their relationship to study treatment or their clinical significance.

Adverse event information will be collected from the date of signed informed consent and up to the end of the study. All ongoing AEs at the end of the study will be followed to resolution or until the Investigator and the Sponsor agree that further follow-up is not required.

An AE is defined as any untoward medical occurrence in a patient enrolled into this study regardless of its causal relationship to study treatment. Patients and parents/legal guardians/caregivers will be instructed to contact the Investigator at any time after the patient/parent/legal guardian signs informed consent, if any symptoms develop while the patient is in the study.

If a patient is hospitalized for a pre-planned elective medical or surgical procedure, or is admitted as an in-patient for a pre-planned observation period post-study drug administration (refer to [Section 6.2.2](#)) this will not be recorded as an SAE unless associated with an untoward medical occurrence that meets the definition of a serious event as outlined in [Section 9.3.1](#) (e.g. bleeding event after surgery that prolongs hospitalization). Such hospitalization must be documented in advance in the patient's medical record and the reason should be described in detail.

A TEAE is defined as any event not present before exposure to study treatment or any event already present that worsens in either intensity or frequency after exposure to study treatment.

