11.2.1 Analysis Populations

The primary efficacy analysis population will be the intent-to-treat (ITT) population, which consists of all randomized patients. All patients will be analyzed according to the treatment to which they are randomized.

The safety population will include all randomized patients who have received at least one dose of the study drug. All patients will be analyzed according to the treatment they have actually received.

The pharmacokinetic population will be a subset of the safety population and include subjects with evaluable pharmacokinetics data.

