15.4 Study Termination

Although the Sponsor has every intention of completing the study, the Sponsor may terminate the study, or close an individual study site at any time for any reason. Some reasons for terminating a study or closing a site may include, but are not limited to, the following:

- The research can no longer meet its stated scientific purpose, and this assessment has been confirmed by the medical ethical review committee which has given a positive assessment of the research
- Severe non-compliance to this protocol as judged by the Investigator and/or the Sponsor
- Due to unforeseen circumstances that prevent continuation of the research

The end of the study is defined as the date on which the last patient completes the last visit (includes follow-up visit).

Upon completion or termination of the study, the medical monitor will conduct site closure activities with the Investigator or site staff (as appropriate), in accordance with applicable regulations, ICH GCP, and SOPs.

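### The adverse-event window has no cut at Week 48, so the by-group TEAE tables can mix placebo time with open-label WVE-210201 time, and no rule covers patients who receive both

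*Combined protocol and SAP*

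**What the plan says.** Section 11.3.4 fixes the window: "On-treatment AEs are AEs that developed or worsened from the first dose of study drug to study completion/discontinuation". All such events go into the TEAE summaries, which are presented by treatment group. Section 11.3.4.1 adds "The denominator for computation of percentages is the safety population within each treatment group". Repeat occurrences of an event count once per patient, at the highest severity and the highest level of relationship.

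On attribution, Section 11.2.1 says of the safety population: "All patients will be analyzed according to the treatment they have actually received". It does not say what this means for a patient who receives two treatments.

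On treatment after the blinded phase, Section 4.1.3 says "Patients randomized to placebo in the Double-blind period will be treated at the matching WVE-210201 dose level", and a footnote to Table 1 in Section 4.2 says "Starting from Week 48, all patients will receive WVE-210201".

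On how long events are collected, Section 9 says "Adverse event information will be collected from the date of signed informed consent and up to the end of the study". Section 15.4 says "The end of the study is defined as the date on which the last patient completes the last visit" and includes the follow-up visit in that.

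Section 3.1 lists "To evaluate the safety of WVE-210201" among the objectives of the double-blind period, and Section 3.2 gives long-term safety as an open-label objective. Section 11.3.2.4 gives the open-label period its own efficacy analysis. Section 11.3 has no matching safety section.

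**The concern.** A placebo-controlled AE table should compare events on drug with events on placebo over the same blinded follow-up. Applied literally, Section 11.3.4 keeps counting for another 48 weeks after the placebo patients have started active drug. If they stay in the placebo column, the table compares immediate with delayed treatment. That is a legitimate comparison, but it is not the blinded drug-placebo contrast.

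The counting rules add to this. A mild event on placebo, followed by a severe and related occurrence of the same event on open-label drug, would appear once, as a severe related event in the placebo column.

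What is at stake is the main AE display of a paediatric trial. If the window is left to be settled after unblinding, the choice will be made with the results in view.

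**Working it through.** **Inputs.** Week 48 is Day 330 (Table 1). The Week 48 infusion is already WVE-210201 (footnote to Table 1). Dosing is weekly, with the last dosing visit at Week 96 (Table 2). The follow-up call comes about 2 weeks later (Section 4.1.5).

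**1. The plan's own figures reproduce.** Duration per patient: 6 + 48 + 48 + 2 = 104 weeks, as the Synopsis states. If Week w starts on Day 7(w − 1) + 1, Week 48 starts on 7 × 47 + 1 = Day 330, as stated.

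**2. End of the window.** Week 96 is 7 × 95 + 1 = Day 666. The call is at about 666 + 14 = Day 680.

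**3. Share of a placebo completer's window spent on WVE-210201.** Days 1 to 329 are on placebo.

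| Measure | On WVE-210201 | Whole window | Share |
|---|---|---|---|
| Days to last dose | 666 − 329 = 337 | 666 | 50.6% |
| Days to follow-up call | 680 − 329 = 351 | 680 | 51.6% |
| Infusions | 96 − 47 = 49 | 96 | 51.0% |

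The share is lower for a placebo patient who leaves during the open-label period, and zero for one who leaves before Week 48.

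**4. Direction and possible size, with patients kept in their randomized group.** Let p0 and p1 be the 48-week risks of an event on placebo and on drug. Let f be the fraction of the drug's excess risk that persists in a second 48 weeks on drug, so that p2 = p0 + f(p1 − p0). Treat the two periods as equal in length and independent.

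- Placebo column: 1 − (1 − p0)(1 − p1)
- Drug column: 1 − (1 − p1)(1 − p2)
- Difference: (1 − p1) × f × (p1 − p0)

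For f between 0 and 1 and p1 above p0, this is smaller than the blinded difference p1 − p0. The documents give no AE rates and no value of f. The risks below are assumptions, shown for f = 1.

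| Assumed p0 v p1 | Blinded period: difference, ratio | Whole window: placebo v drug | Whole window: difference, ratio |
|---|---|---|---|
| 2% v 10% | 8 points, 5.0 | 11.8% v 19.0% | 7.2 points, 1.6 |
| 5% v 20% | 15 points, 4.0 | 24.0% v 36.0% | 12 points, 1.5 |
| 10% v 30% | 20 points, 3.0 | 37.0% v 51.0% | 14 points, 1.4 |

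At f = 0.5 the whole-window differences halve. At f = 0 they vanish, but only because f = 0 assumes it.

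**5. The as-received rule does not settle the matter.** A placebo completer has received both treatments. There are three ways to class him:

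- *Placebo throughout:* steps 3 and 4 apply.
- *WVE-210201 throughout:* 329 days of placebo events enter the drug column, and the placebo column keeps only patients who never had an open-label infusion.
- *Split at the switch:* he belongs to two groups, with about 48 weeks in each. Section 11.3.4.1 gives one safety-population denominator per group and none by period.

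Each needs a rule that the plan does not state.

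**6. The same gap within the active arms.** Section 11.5.1 allows 3 mg/kg patients to be moved to 4.5 mg/kg after a dystrophin interim analysis. It says how they are handled in clinical endpoint analyses but not in safety tables. At 1:1:2:2, the first 30 patients include about 30 × 2/6 = 10 on 3 mg/kg, and the first 70 include about 70 × 2/6 = 23. More could be affected if enrolment continues while results are awaited. These patients stay on active drug, so only the by-dose AE comparison is involved.

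**The case against.** The strongest reply is that dilution follows from one reading only. Section 11.2.1 assigns safety patients by treatment received, so open-label events might be credited to WVE-210201, leaving the placebo column clean. It can be added that Sections 3.1, 3.2 and 4.3 separate the objectives and endpoints by period. The protocol also sometimes uses study conclusion where the Synopsis speaks of the end of the double-blind period, and Section 15.4 defines a trial-level date, not a patient's completion. Finally, a separate SAP may hold the period rules.

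Part of this stands. The dilution is conditional on the reading, and a period split in the SAP would largely answer the point. The rest does not remove it. The as-received rule is silent on patients who receive both treatments, and splitting them needs a denominator that the tables lack. Separate objectives show intent but set no AE window. Section 4.1.4 provides early-termination visits for both periods, and Section 9 collects events to the end of the study, so completion is hard to read as Week 48. Sections 11.5.1 and 11.5.2 defer thresholds and enrolment targets to the SAP, whereas Section 11.3.4 defers nothing.

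A data cut when the last patient reaches Week 48 would not help either, because earlier enrollees would already have open-label exposure.

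A reader might go further and infer that infusion-associated reactions would be masked almost completely. Section 6.2.3 does not support that. It reports such reactions in studies of WVE-210201 or placebo, and shows neither clustering at first exposure nor an excess on drug.

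**Conclusion.** The concern holds in a conditional form. Section 11.3.4 has no Week 48 cut. If patients keep their randomized group, about 51% of a placebo completer's counted window is on WVE-210201, and the drug-placebo contrast is diluted for events whose risk the drug raises. If they are classed by treatment received, there is no rule or denominator for those who received both. The 51% rests on the schedule alone and applies to completers. The amount of dilution rests on AE rates that the documents do not give, so the risks and differences under the working are illustrations.

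Two stronger conclusions are not supported. First, the placebo-controlled safety comparison is not lost: onset date and time are recorded (Section 9.1), full AE listings are planned, the DMC sees unblinded safety data during the double-blind period, and by-visit laboratory summaries already separate the periods. Second, the possible move from 3 to 4.5 mg/kg does not weaken the drug-placebo contrast; it bears only on the comparison between doses.

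**What to change.** - **Section 11.3.4:** define the double-blind TEAE window as first dose up to, but not including, the first open-label WVE-210201 infusion (scheduled at Week 48). For a patient who never has one, end it at the earlier of study discontinuation and the Week 48 visit date. A placebo completer then contributes 329 days and 47 infusions, none of them active.
- **Between-arm tables:** base the AE tables and the matching exposure tables on that window. The exposure definition in Section 11.3.1 has no period cut either.
- **Open-label events:** tabulate them separately by sequence (placebo to WVE-210201; continuing WVE-210201).
- **Section 11.2.1:** state that, for the between-arm tables, treatment received means treatment received in the double-blind period. State also how the AEs of 3 mg/kg patients moved under Section 11.5.1 are attributed in the by-dose tables.
- **SAP:** if it already splits safety by period, align Section 11.3.4 with it.

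The cost is wording and one extra set of tables. No new data are needed, because onset date and time are already collected, and they also place events that occur on Day 330 before or after the infusion. The change should be made before unblinding.
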